The diagnosis of AF, as well as that of other complications, is often made when the patient is symptomatic, requiring immediate and perhaps more aggressive intervention than if an earlier diagnosis had been made. Treatment is generally decided based on the size of the leak, the degree of local contamination, and the associated severity status of the patient. Thus, early diagnosis of AF by clinical, radiological and/or endoscopy is essential to provide immediate treatment through antibiotic therapy, placement of a feeding tube, application of endoscopic therapies, percutaneous drainage of collections, etc., possibly reducing the rate surgical review. For all these reasons, early prediction, diagnosis and treatment of possible major complications (Clavien-Dindo greater than 3), especially AF, are essential to improve the results and prognosis of the disease (6).

Different studies have investigated the usefulness of the use of markers, both pre and postoperative, to predict possible postoperative complications. Recent studies have evaluated different markers in early postoperative stages as predictors of AF and other major complications. These include C-reactive protein (CRP) (7), white blood cell count (RGB) (8), serum albumin (9), tumor necrosis factor  $\alpha$  (TNF  $\alpha$ ), interleukins 1 and 6, the CRP- albumin (CAR) (10-13), modified Glasgow Prognostic Score (mGPS), platelet/lymphocyte ratio and neutrophil/lymphocyte ratio (4) among others.

After carrying out a thorough bibliographic search, the small number of quality prospective studies in this area has been observed, most of them being retrospective or systematic reviews of retrospective studies.

CRP is one of the most studied inflammatory markers related to AF. It is mainly synthesized in the liver in response to proinflammatory cytokines, as an acute phase response protein, and its levels correlate with the severity of inflammation (14). CRP levels increase after surgery and commonly peak after 48 hours (15,16), subsequently decreasing in patients with an uncomplicated postoperative course. Therefore, CRP is especially valuable as a negative test, and a normal or falling CRP level on the third and fifth postoperative days (POD) can help predict which patients are not likely to develop AF (17). Although several prospective

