Peritoneal levels of IL-6 and TNF $\alpha$  were significantly higher in patients with colorectal anastomosis leak compared to patients without leak in some studies and may contribute to their early detection (18), having found that increased levels Serum IL-6 is a predictor of AF in gastrointestinal surgery (24).

In the retrospective study of 330 patients carried out by Yansen et al (25), the neutrophil-lymphocyte ratio (NLR) was used as a biochemical marker. The incidence of AF was 16%, 47.2% of them being treated by surgery. An increasing trend in RLN was significantly associated with the need for surgical intervention, with the mean leak diagnosis time being 7 days and 49.1% being grade III AF. An NLR cut-off value of 10 at the 3rd POD had 74.5% sensitivity, 58% specificity, 25% positive predictive value, and a value of less than 10 had 92.4% negative predictive value for leaks. The results of this study concluded that the value of NLR is more relevant in its negative predictive values and helps in making postoperative decisions with more confidence. On the contrary, an increasing trend of RLN between 1st and 3rd DPO is an independent factor of AF that should be alerted to its suspicion.

Findlay et al (26) developed a prospective study of 326 patients where it was concluded that the use of elevated inflammatory markers is more useful in diagnosis than in prediction, therefore, these parameters do not seem to be very useful for diagnosis and management. early AF. Similar conclusions were obtained in the work published by Liesenfeld et al (20) where the CRP, RGB and NU scores are not recommended as independent markers for the prediction of AF after transthoracic esophageal resection. Another retrospective study by Sugimoto et al (13) of 295 patients analyzed preparatory inflammatory and nutritional markers and studied their relationship with the appearance of postoperative AF in esophageal cancer. The study compared the predictive capacity of preoperative CAR, nutritional prognostic index (PNI), and mGPS for AF, and identified that an elevated value of preoperative CAR ( $\geq 0.0139$ ), but not PNI or mGPS, is a useful indicator for predict the occurrence of AF after esophagectomy. The results of their study suggest that preoperative CAR is a promising predictive marker of AF.

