## OBJECTIVES

Based on the hypothesis of the study, the main and secondary objectives of this study are established:

- Main goal:

\*Design a predictive model based on clinical and analytical variables that allow identifying patients with a high risk of anastomotic leak (main variable) during the postoperative period of esophagogastric surgery.

- Secondary objectives:

\* Design a predictive model based on clinical and analytical variables that allow identifying patients at high risk of other major complications (Clavien-Dindo greater than 3) during the postoperative period of esophagogastric surgery.

\* Individually describe the postoperative evolution of the clinical and analytical parameters studied in patients without major complications or AF and those who did suffer from any of them.

\* Describe the complications and types of AF diagnosed in the study.

\* Assess the day AF was diagnosed and the treatment used for its possible resolution.

\* Assess the day AF was diagnosed and hospital stay.

\* Compare the preoperative Glasgow prognostic score (mGPS) and the biochemical value of inflammatory markers (CRP, Interleukin 6 (IL-6) and procalcitonin) and the appearance of AF.

\* Assess the AF resolution capacity of each technique used.

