## **7.- Follow up**

The patient will be monitored during the first 90 postoperative days, compiling all the specific variables of this study and the possible complications and mortality that occurred in this period.

During the immediate postoperative period, apart from the care applied routinely in each center, patients should be evaluated daily and the clinical and laboratory variables specified later should be collected on days 1, 2, 3, 4 and 6 postoperatively. In the same way, in this postoperative course, the possible complications that appeared during the hospital stay will be compiled.

Subsequently, if the patient is discharged from the hospital, a follow-up will be carried out in the outpatient consultations at 30 and 90 days to evaluate the possible complications that appear in this period and other variables studied will be completed.

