### **8.2.2.- PREOP (PRE-OPERATIVE) and POST-OPERATIVE DAYS (DAY 1, DAY 2, DAY 3, DAY 4 AND DAY 6)**

These boxes include the variables collected PREOPERATIVELY and during the established postoperative days. These variables are:

- HR (HEART RATE): continuous variable expressed in beats per minute.
- RR (RESPIRATORY RATE): continuous variable expressed in breaths per minute.
- Ta (TEMPERATURE): continuous variable expressed in OC.
- VAS (VISUAL ANALOGUE SCALE): Scale used to assess the degree of pain. Ordinal variable from 1 to 10.
- TAS (SYSTOLIC ARTERIAL PRESSURE): continuous variable expressed in mmHg.
- DBP (DIASTOLIC ARTERIAL PRESSURE): continuous variable expressed in mmHg.
- SAT O2 (OXIGEN SATURATION): continuous variable expressed in %.
- DIURESIS (DIARIES VOLUME OF DIURESIS): continuous variable expressed in ml/day.
- LEUKES (LEUKOCYTES): continuous variable expressed in number/ $\mu$ L.
- LYMPHOS (LYMPHOCYTES): continuous variable expressed in number/ $\mu$ L.
- NEUTRAL (NEUTROPHILS): continuous variable expressed in number/ $\mu$ L
- HB (HEMOGLOBIN): continuous variable expressed in g/dL.
- PLATELET (PLATELET): continuous variable expressed in number/ $\mu$ L
- CREATININE (CREATININE): continuous variable expressed in mg/dL.
- PROTEINS (PROTEINS): continuous variable expressed in g/dL.
- ALBUMIN (ALBUMIN): continuous variable expressed in g/dL.
- CRP (C-REACTIVE PROTEIN): continuous variable expressed in mg/L.
- PROCAL (PROCALCITONIN): continuous variable expressed in ng/mL.
- IL 6 (INTERLEUKIN 6): continuous variable expressed in pg/ml.
- QUICK (QUICK INDEX): continuous variable expressed in %.

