### 2.- Data análisis

The statistical study will be carried out with the help of the SPSS® version 23.0 software for Windows, using the MATLAB® programming environment for the preparation of the predictive model based on artificial neural networks (ANN).

In the first place, a descriptive analysis will be carried out, both of the sociodemographic and clinical variables, as well as of the analytics and the results of the study.

To describe the quantitative variables that follow a normal distribution, the mean and standard deviation will be used, and the median and interquartile range for those that do not follow a normal distribution, as well as histograms with normality curves for their graphical description.

For the qualitative variables, frequencies and percentages will be used, using bar graphs and/or sectors for the graphic description of those with greater relevance.

A univariate study will be performed to relate the variables studied with the appearance of AF and major postoperative complications. For this, different tests will be used depending on the variable to be studied:

- a) Normal categorical variables: Chi-square test or Fisher's exact test.
- b) Normal continuous variables: Student's t-test.
- c) Non-normal continuous variables: Mann-Whitney U test.

In the results obtained from the univariate study, those variables that show a  $p < 0.1$  after the application of the corresponding tests will be considered as related or candidates to predict AF or major

complications. This value will be considered more conservative, different from the conventionally accepted value of 0.05, with the intention of not ruling out potential variables that could have some influence on the results of the study.

Once the univariate study has been completed, a multivariate study will be carried out, using the logistic regression (RL) method. To do this, a recoding of the variables will be carried out, transforming the categorical variables into dummy variables. It will be verified that the variance inflation factor (VIF) is less than 2 in all cases, thus ruling out important problems of collinearity between the variables.

On the other hand, a predictive model based on artificial neural networks (ANN) will also be developed, using a Multilayer Perceptron, a multilayer neural network of forward connections, without recurrent connections and supervised learning.

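### A VIF limit of 2 for every variable is an ill-suited criterion for a prediction model, and trend information may be lost if the limit is met by deleting serial markers

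*Combined protocol and SAP*

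**What the plan says.** In section 2 (data analysis) of the data collection and analysis chapter, variables with a univariate p below 0.1 become candidates for a logistic regression with dummy coding. The collinearity rule follows: "It will be verified that the variance inflation factor (VIF) is less than 2 in all cases", with the purpose "thus ruling out important problems of collinearity between the variables". The section gives no action if a VIF is 2 or more. It also does not say whether the daily values enter one by one, as changes, as slopes or as ratios. The neural network, described next, carries no VIF condition.

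The main objective is a model that identifies patients at high risk of leak, so the aim is prediction.

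Section 7 (Follow up) says that the clinical and laboratory variables "should be collected on days 1, 2, 3, 4 and 6 postoperatively". Section 8.2.2 lists 20 of them and adds a preoperative value: "These boxes include the variables collected PREOPERATIVELY and during the established postoperative days". The list contains related pairs, such as leukocytes and neutrophils.

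The Introduction treats change over days as informative. On the neutrophil-lymphocyte ratio it reports that "an increasing trend of RLN between 1st and 3rd DPO is an independent factor of AF". On CRP it gives weight to "a normal or falling CRP level on the third and fifth postoperative days". It also reports a smaller fall in white cells after day 2 in patients with a leak.

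**The concern.** VIF = 1/(1 − R²), where R² comes from regressing one predictor on the others. A limit of 2 therefore means R² below 0.5, and any pair correlated at 0.71 or more fails. Serial values of one marker can easily be correlated that strongly.

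Collinearity widens the standard errors of single coefficients. It need not reduce the accuracy of predictions in similar patients. A limit that the same predictions can pass or fail, depending on how the variables are written, does not test what this model is for.

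The practical risk lies in how the analysts make the check pass. If they delete days, the model may lose the movement between days that the background points to. Which day or marker survives would then rest on a choice made after the data are seen.

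**Working it through.** The plan gives no calculation on this point and no correlations, so the correlations below are assumptions, varied over a range. The limit of 2 and the measurement days come from the plan. The sample size of 847 (section 4) is used only to set the size of the simulation in step 5.

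1. **Five raw days, correlation decaying with time (AR-1, adjacent-day r).** A day with neighbours one day away on both sides has VIF (1 + r²)/(1 − r²). Setting this equal to 2 gives r² = 1/3, so r = 0.58. VIFs for days 1, 2, 3, 4 and 6:
   - r = 0.5: 1.33, 1.67, 1.67, 1.40, 1.07 (none fails)
   - r = 0.7: 1.96, 2.92, 2.92, 2.28, 1.32 (three fail)
   - r = 0.8: 2.78, 4.56, 4.56, 3.47, 1.69 (four fail)
   - r = 0.9: all five fail

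   With equal correlation between all five days, the limit is crossed at about 0.59.

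2. **Leukocytes with neutrophils.** At r = 0.9, VIF = 1/(1 − 0.81) = 5.3.

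3. **Dependence on coding.** For a dummy with proportion p and a reference group with proportion p0, VIF = (1 − p)(1 + p/p0). Take four categories of 30%, 30%, 30% and 10%.
   - With the 10% group as reference, each dummy has 0.7 × (1 + 3) = 2.8 and fails.
   - With a 30% group as reference, the dummies have 0.7 × 2 = 1.4 and 0.9 × 1.33 = 1.2, and all pass.

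   The fitted predictions are the same in both cases.

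4. **Cost of deletion, by formula.** With normal markers, AUC = Φ(D/√2) and D² = d′C⁻¹d, where d is the vector of mean differences in SD units. Take three consecutive days with d = (0, 0.3, 0.6).
   - Equal correlation 0.8: D² = 5 × [0.45 − (0.8/2.6) × 0.81] = 1.004, AUC 0.761. Any two days have VIF 1/(1 − 0.64) = 2.78, so only one raw day can stay. The last day alone gives Φ(0.6/√2) = 0.664, a loss of about 0.10.
   - Same case, last value plus change from the first day: D² = 0.36/(1 − 0.64) = 1.0, AUC 0.760. The two terms correlate at √0.1, so VIF = 1/(1 − 0.1) = 1.11.
   - AR-1 at 0.8: all three days give D² = 0.09/0.36 + 0.36²/0.36 = 0.610. The first and third days alone (correlation 0.64, VIF 1.69) give 0.36/(1 − 0.4096) = 0.610. AUC is 0.710 either way. A simulation under AR-1 with 200,000 patients and 15% leak gave losses of 0.003 to 0.009.
   - Limit of that result: it holds for a steady trend. With d = (0, 0.3, 0.6, 0.6, 0.6) on the five study days and AR-1 at 0.8, D² = 0.25 + 0.36 + 0.04 + 0.079 = 0.729 and AUC is 0.727. Days 1 and 3 alone give 0.710, a loss of 0.017.

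5. **Cost of deletion, by simulation.** Two days of one marker, 847 patients, 15% leak (assumed; the Introduction cites 16% in one retrospective series), 60 replicates, AUC in 50,000 new patients. The three AUC columns run from level only, through level and change equal, to change dominant.

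| r | VIF, both raw days | VIF, latest + change | AUC, both days | AUC, later day only |
|---|---|---|---|---|
| 0.71 | 2.02 | 1.17 | 0.701 / 0.712 / 0.716 | 0.689 / 0.699 / 0.647 |
| 0.80 | 2.78 | 1.11 | 0.699 / 0.712 / 0.719 | 0.692 / 0.689 / 0.647 |
| 0.90 | 5.26 | 1.05 | 0.704 / 0.719 / 0.720 | 0.699 / 0.687 / 0.622 |

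Latest value plus change has the same AUC as both raw days to three decimals. Deletion costs about 0.005 to 0.03 when level dominates or weighs equally, and 0.07 to 0.10 when change dominates.

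**The case against.** The strongest reply is that the plan only promises to verify the VIF. A reader might infer that the rule forces predictors out of the model. The text does not support that: it contains no deletion rule and does not say that all raw days enter together. Change, slope or a ratio such as neutrophils to lymphocytes can carry the trend in a single variable, and latest value plus change meets the limit. The fall in AUC from 0.76 to 0.66 is therefore not an effect of the rule itself. It arises only if days are deleted and nothing is recoded. This stands.

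Even raw values can survive. Under AR-1, days 1 and 3 correlate at r², so the pair passes while r⁴ is below 0.5, that is, up to r of about 0.84. At r = 0.7, days 1, 3 and 6 can all stay. This also stands, and it is why the harm is stated as conditional.

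A reader might also infer that the rule tilts a comparison of logistic regression with the neural network, because only the regression carries it. The documents plan no head-to-head comparison. They say only that a network model will be developed as well. The network is untouched by the rule, so harm to the main objective as a whole is not shown.

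Finally, limiting redundant predictors has some purpose in an unpenalised regression, particularly one meant for centres that manage patients differently. That is a fair reason to control redundancy. It does not justify this cut-off, whose result can change with the choice of reference category.

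**Conclusion.** The point holds in a limited form. A universal VIF limit of 2 is strict and measures something other than predictive accuracy. Raw serial values would breach it at adjacent-day correlations of about 0.58 or more, and same-day leukocytes and neutrophils very probably would. The plan leaves open both the coding of serial markers and the response to a failed check.

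The loss occurs only if variables are deleted without recoding. Its size then depends on correlations and a signal shape that the documents do not give: below 0.01 in AUC for a steady trend with decaying correlation, and up to about 0.10 when days are equally and strongly correlated and the signal lies in the change. This is a cheap improvement to the analysis plan. It does not show that the planned model fails.

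**What to change.** Make three changes in the data analysis section:

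- Remove VIF below 2 as a requirement for the logistic model. Keep VIF as a descriptive check only, in its generalised form for sets of dummies.
- Specify that each serial marker enters as its latest value plus its change from a named earlier day.
- Fit the logistic model with a ridge or elastic-net penalty, tuned by cross-validation.

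The cost is a change of wording and a standard penalised-regression routine. No further data or patients are needed, because all the values are already collected. The drawback is that penalised coefficients are less easy to read as odds ratios.

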## STAGES OF DEVELOPMENT AND DISTRIBUTION OF TASKS

The project will be developed at a national level and all the centers that wish to include patients who meet the recommended inclusion and exclusion criteria will participate in it and will follow the following stages of development:

### **1.- Idea and creation of the project**

This project has been developed jointly by members of the General Surgery and Digestive System Services of the La Fe University and Polytechnic Hospital in Valencia and the Juan Ramón Jiménez Hospital in Huelva.

### **2.- Presentation of the project**

The project will be presented to the Spanish Association of Surgeons, Esophagogastric Surgery section of the same and to all the Spanish centers that are candidates to participate through the cover letter that is attached in the Annexes section (Annex 3).

### **3.- Duration of the study**

It is estimated that the approximate total duration of the study will be 2 years, in which each center will carry out the recruitment of patients and their postoperative follow-up for 90 days. In each center, patients who meet the inclusion and exclusion criteria consecutively and for one year will be included. The coordinators of each hospital center must inform the general coordinators of the study of the date of inclusion of the first patient in the study, as well as any problem that occurred in the incorporation of cases and data collection.

### **4.- Distribution of tasks**

The different tasks to be carried out during the study will be distributed as follows:

4.1.- The coordinators of the study will be [name] and [name] and they will be in charge of coordinating with the hospitals involved. These features include:

4.1.1.- Publicity and dissemination of the project

4.1.2.- Sending the necessary documents to carry out the study:

—> Invitation letter

—> Explanatory document of the research project

—> Database to complete

—> Instructions for filling the database and definition of variables

—> Approval of the project by the Research and Ethics Committee of one of the centers included in it.

—> Informative document and informed consent for the inclusion of patients in the study.

4.1.3.- Contact with those responsible for the study at each hospital, in order to resolve possible doubts and to control and monitor the data entered.

4.1.4.- Reception, grouping, revision and homogenization of the data collected, performing the calculations of the necessary variables and processing the information for analysis and obtaining results.

4.1.5.- Periodic information to the participating centers on the status of the study, number of cases collected, etc.

4.2.- Those responsible for the study in each center

The inclusion of patient data in the study database will be carried out by those responsible for the study in each center and the professionals they consider appropriate to help them. Each person in charge at each center will be in charge of presenting the project and obtaining authorization from the Research and Ethics Committee of their hospital to be able to carry it out. Once submitted and approved, each hospital must collect data according to the established instructions, obtaining the informed consent of all patients in the study, which must be stored safely.

4.3.- Responsible for the statistical study and creation of the predictive model and application for mobile devices

The work of the descriptive and analytical statistical study of the series, as well as the creation of the predictive models and the development of the application for mobile devices and/or web for the application of the predictive model will be carried out by members of the Intelligent Data Analysis Laboratory. of the Department of Electronic Engineering of the Higher Technical School of Engineering of the University of Valencia.

### **5.-Schedule:**

The schedule of the study is presented schematically below:

5.1.- Conceptual or theoretical phase: choice of topic, literature review, goal setting, hypothesis development: 1 month (November 2021).

5.2.- Design phase: choice of design and choice of variables, development of database and schedule: 1 month (December 2021).

5.3.- Evaluation, approval and authorization of the study by the Research and Ethics Committee of one of the collaborating centers (January 2022).

5.4.- Dissemination and adhesion phase: presentation and dissemination of the project to the Spanish Association of Surgeons, the Esophagogastric Surgery Section and all the centers that wish to collaborate in it (January 2022). The centers may gradually join the study until June 2022.

5.5.- Empirical phase: recruitment and collection of patient data, surgical intervention, results and follow-up. In each center, the data of consecutively operated patients during the period of 1 year from the inclusion of the first case will be collected. Access to the medical records of participating patients will only be allowed to researchers at each center. The data will be collected in each of the participating hospitals and the custody of the same will be the responsibility of the main coordinator or person in charge in each center, who will be in charge of guaranteeing that no identifying data of the patients is transmitted. The data will be encrypted by generating a unique code that will be the only one that will be sent to the central coordination team.

5.6.- Interpretive phase: once the recruitment period for all the centers has closed, the data will be analyzed, the results discussed and compared with other studies. The predictive model described and reason for the study will be created. The estimated duration of this phase will be 3 months.

5.7.- Communicative phase or dissemination of results. Communication of the results to all the participating centers and writing and preparation of scientific articles and communications to congresses (national and international scope). All those responsible for each center will appear as co-authors in all the works and communications published, establishing the order of appearance in them based on the number of cases included in the study. The estimated time for the preparation of this material will be approximately 1 month.

5.8.- Creation and dissemination of the predictive tool. Creation of an application for mobile devices and/or web page where the data of new cases can be entered prospectively, obtaining the prediction of a possible AF or major postoperative complication in each new patient. The estimated time for the creation of this tool will be approximately 3-4 months. Once it has been created and its correct functioning has been tested, it will be disseminated. With the new data entered, an evaluation of the effectiveness and profitability of the model will be carried out, which will supposedly improve with the introduction of more data.

5.9.- Development of sub-studies: once the previous stages have been completed, different sub-studies proposed by the project collaborators will be developed. The collaborator or collaborators who have

proposed the sub-study will be the coordinator and responsible for it, appearing as the first or first signatories in the communications and publications that arise from its realization.

